The proposed study would provide rigorous clinical, MRI, digital and biomarker data demonstrating the effect of ofatumumab in a naïve RRMS population at first diagnosis and would provide the first data relative to healthy controls, identified data gaps in the US. The very early MS young adult population in this study will consist of treatment naïve RRMS patients that are within 6 months of diagnosis at the time of study entry. Detailed data will be collected within the first month to document a rapid response to therapy. Further, a HC group will be used to analyze select endpoints vs ofatumumab (e.g., brain atrophy) with the strategy of showing normalization of brain structural/functional changes. This would also highlight the need for high efficacy therapy very early in the course of the disease as the extension data of up to 30 months would potentially show stabilization long term.

2 Objectives, endpoints and estimands

Table 2-1 Objectives and related endpoints

[figure not shown]
Objective(s)	Endpoint(s)

Primary Objective(s)
 
 The primary objective is to explore the impact of ofatumumab (OMB) on the ability to achieve No Evidence of Disease Activity (NEDA-3) status in treatment-naïve, very early RRMS patients over an 18 month, open-label study period after a re-baseline of MRI at 6 months 	
Endpoint(s) for primary objective(s)
 
 NEDA-3 (Relapse-free, 3-month clinical disability progression-free, MRI activity-free) in Months 6 to 18 (yes/no)

Secondary Objective(s)
 
Evaluate the effect of ofatumumab on various clinical (NEDA, disability, relapse) metrics at 18 months
	
Endpoint(s) for secondary objective(s)
 
Baseline and months 6, 12, 18, 30 (T1 Gd)

 Evaluate the effect of ofatumumab on conventional MRI metrics, with MRIs at 	

- Number of relapses
- 3-month Disability Worsening-free (yes/no)
- NEDA clinical in Months 6 to 18 (yes/no)
- NEDA radiological in Months 6 to 18 (yes/no)
- Change from Baseline in Conventional MRI metrics
(Gd+ lesion number, new Gd+ lesion number, Gd+ lesion volume, T2 lesion

Objective(s)	Endpoint(s)
@ Baseline, month 6, 18 and T1/T2 @ every timepoint)	number (Baseline), New/enlarging T2 lesion number (post-Baseline), T2 lesion volume, new unenhancing T1 lesion number, T1 unenhancing lesion volume)

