4.5 Risks and benefits

The risk to participants in this trial will be minimized by compliance with eligibility criteria, close clinical monitoring, avoidance of prohibited treatments, adherence to protocol requirements, and Investigator guidance regarding specific safety areas. In addition, the study has been designed to minimize site visits (during COVID pandemic) and reduce the number of MRI scans using gadolinium. Safety data from the pivotal Phase 3 program are available and the benefit/risk profile for ofatumumab treated patients with RMS is assessed as favorable.

Clinical experience with ofatumumab in RRMS patients comes from four Phase 2 studies and the two Phase 3 clinical trials, where a total of 1537 RMS patients have been exposed to ofatumumab (Phase 2 studies: iv: N=38; and sc: N=553; Phase 3 studies sc N=946). No unexpected safety findings were observed in MS patients who received ofatumumab in the two completed Phase 2 studies and two ASCLEPIOS Phase 3 studies.

Briefly, in the 48-week, placebo-controlled, cross-over study (cross-over at 24 weeks) of iv doses of ofatumumab up to 700mg, adverse events reported more frequently on ofatumumab vs placebo included: rash, throat irritation, erythema, fatigue, viral infection and flushing (Sorensen et al., 2014). In the placebo-controlled, dose-ranging study of ofatumumab administered at sc doses up to 60mg every 4 weeks for up to 24 weeks, injection related reactions were observed more frequently in the overall ofatumumab group (Bar-Or et al 2018). In the ASCLEPIOS I and II studies, ofatumumab demonstrated a favorable safety profile with no unexpected safety signals, no imbalance in adverse events or serious adverse events (SAEs), rates of infection (including serious infection), or malignancy when compared to teriflunomide. In these studies, systemic injection-related reactions were reported in 20.6% of patients on ofatumumab and in 15.3% of patients on teriflunomide. 99% of all reported systemic injection reactions were mild to moderate (Grade 1-2) and limited to the first injection (Hauser et al., 2020, Kesimpta[®], PI).

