O = Ofatumumab participant

H = Healthy Control

X = assessment to be recorded in the clinical database or received electronically from a vendor

S = assessment to be recorded in the source documentation only

■ [Redacted]

² Relapse assessment will be performed in scheduled, as well as unscheduled visits as deemed necessary by the Investigator or designee. Assessment can be done on site or via remote procedures

³ Urine β-hCG will be conducted monthly, at home, as well as, at defined clinical visits (scheduled and unscheduled)

[Redacted]

⁴ Assessment during an unscheduled visit will be performed as deemed necessary by the investigator, **except** for vital signs and evaluation of AE, which are mandatory at each visit

⁶ Participants are not required to come to the study site. Remote contact with participants, by site staff around the time of at-home, self-administration of ofatumumab should query about any new or worsening symptoms warranting an unscheduled visit, MS relapse, compliance with study treatment [REDACTED], adverse events, and compliance with contraception requirements (when applicable). The method of contact can be via telephone, email, video conference or text message depending on the preference of each participant

⁷ For the first injection, vital signs should be obtained 30-60 minutes before sc injection and again approximately 60 minutes post-injection

⁸ All lab assessments should be taken prior to dosing at the Day 1 visit. For any later biomarker visits, if the visit coincides with the day the monthly injection is scheduled, the subject should not take the injection in the morning before coming to the site so that the biomarker sample can be drawn before the injection

⁹ Labs must be drawn to allow adequate time for results to be obtained before first study drug administration to ensure participant's eligibility

¹⁰ Urine dipstick: If abnormal send full urinalysis to central laboratory

¹² Data for safety follow-up visit will be captured in source documentation only. Safety follow-up participants are not required to come to study site and lab assessments should be done locally

¹³ Only for participants continuing onto the 12-month open-label extension period

¹⁴ Gadolinium will not be given to healthy controls and gadolinium enhanced T1 MRI imaging will not be conducted in healthy controls

¹⁵ The C-SSRS must be administered at either screening or baseline, then at every on-site visit thereafter until End of Study (EOS)

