**Table 1 Study objectives and endpoints**

Objective(s)	Endpoint(s)

Primary Objective(s)
 
 
The primary objective is to explore the impact of ofatumumab on the ability to achieve No Evidence of Disease Activity (NEDA-3) status in treatment-naïve, very early RRMS participants over an 18 month, open-label study period after a re-baseline of MRI at 6 months
 
	
Endpoint(s) for primary objective(s)
 
 
NEDA-3 (relapse-free, 3-month clinical disability progression-free, MRI activity-free) in Months 6 to 18 (yes/no)
 

Secondary Objective(s)
 
 
Evaluate the effect of ofatumumab on various clinical (NEDA, disability, relapse) metrics at 18 months
 
Evaluate the effect of ofatumumab on conventional MRI metrics, with MRIs at Baseline and Months 6, 12, 18, 30 (T1 gadolinium (Gd) @ Baseline, Month 6, 18 and T1/T2 @ every timepoint)
 
Evaluate the effect of ofatumumab on patient reported outcomes (PROs) (Quality of Life in Neurological Disorders [NeuroQOLTM], Patient Determined Disease Steps [PDDS])
 
Evaluate the effect of ofatumumab vs healthy controls on 1) whole brain and regional atrophy measured at Month 18/30 after re-baseline at 6 months; and 2) regional atrophy measured 18/30 months from Baseline
 
Evaluate the safety and tolerability of ofatumumab
 
	
Endpoint(s) for secondary objective(s)
 
 
Number of confirmed relapses in Months 6 to 18
 
3-month disability worsening-free in Months 6 to 18 (yes/no)
 
NEDA clinical in Months 6 to 18 (yes/no)
 
NEDA radiological in Months 6 to 18 (yes/no)
 
Change from baseline in conventional MRI metrics (Gd+ lesion number, new Gd+ lesion number, Gd+ lesion volume, T2 lesion number (Baseline), new/enlarging T2 lesion number (post-Baseline), T2 lesion volume, new/enlarging T2 lesion volume, new unenhancing T1 lesion number, T1 unenhancing lesion volume)
 
Change from baseline in PROs (NeuroQOLTM, PDDS) (also obtained in healthy controls)
 
Brain volume assessment (whole brain and regional) (also obtained in healthy controls)
 
Adverse events, laboratory data, physical examination, and vital signs (also obtained in healthy controls)
 

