## 2.2 Analysis sets

The Full Analysis Set (FAS) will include all enrolled participants that received any study drug.

The Safety Analysis Set (SAF) will be the same as the FAS.

The Healthy Control Analysis Set (HCAS) will include all enrolled healthy control participants. This analysis set will be used in the analysis of data collected from healthy control participants.

The modified FAS (mFAS) will include all participants in the FAS except for those who discontinued treatment prematurely prior to Month 18 for reasons other than lack of efficacy or death, or those who completed their Month 18 visit but missed relapse/EDSS/MRI (Gd+ or

new/enlarging T2 lesions) at Month 6, 12 or 18, unless they showed disease activity (i.e., MRI activity after Month 6 through 18 or relapse/3-month clinical disability progression between Months 6 and 18). The mFAS will be used for NEDA-3, NEDA clinical and NEDA radiological efficacy analyses.

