**Table 7 Criteria for clinical disability progression based on change from Month 6 in EDSS (global assessment scale)**

EDSS at Month 6	Clinical disability progression criterion
0	≥ +1.5
1 to 5	≥ +1
≥5.5	≥ +0.5

- MRI activity-free is defined as no Gd+ lesions on any MRI scan (scheduled or unscheduled) after Month 6, or new/enlarging T2 lesions compared to Month 6 on any MRI scan (scheduled or unscheduled) after Month 6.

The primary estimand is described by the following attributes:

- **Population:** Defined through appropriate inclusion/exclusion criteria to reflect the targeted population. Young adult and very early RRMS (defined as within 6 months of diagnosis of clinically definite RRMS) patients that are DMT treatment naïve.

- **Variable:** NEDA-3 (relapse-free, clinical disability progression-free, MRI activity-free) in Months 6 to 18 (yes/no)
- **Treatment of interest:** An initial dose regimen consisting of doses administered at Baseline/Week 0 (Day 1), followed by Week 1 (Day 7), Week 2 (Day 14), and then every month thereafter, beginning at Week 4 (Month 1) until Month 18. All doses of ofatumumab will be given subcutaneously via an auto-injector at a dose of 20 mg. Healthy controls will be used for comparison purposes and will not receive study treatment.
- **Intercurrent event:** Treatment discontinuation due to lack of efficacy or death
- **Summary measure:** Proportion of participants achieving NEDA-3 in Months 6 to 18

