### 2.5.3 Handling of intercurrent events

Handling of treatment discontinuations will follow composite variable strategy. For treatment discontinuation prior to Month 18 due to lack of efficacy or death, NEDA-3 and associated endpoints will be considered as “non-response”; if treatment discontinuation prior to Month 18 is due to reasons other than lack of efficacy or death, or if the Month 18 visit was completed but relapse/EDSS/MRI (Gd+ or new/enlarging T2 lesions) was missed at Month 6, 12 or 18, and disease activity was not shown (i.e., MRI activity after Month 6 through 18 or relapse/3-month clinical disability progression between Months 6 and 18), the participant will be excluded from mFAS for all NEDA-3 and associated endpoints efficacy analyses and thusly out of scope for intercurrent events handling; the rest of the participants had disease activities in Months 6 to 18, and NEDA-3 and associated endpoints for those participants will be considered as “non-response”.

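### The primary analysis set (mFAS) can exclude activity-free completers for a gadolinium reading that is not scheduled (Month 12) or cannot change NEDA-3 (Month 6)

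*SAP*

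**What the plan says.** **The exclusion rule.** SAP 2.2 leaves out of the mFAS "those who completed their Month 18 visit but missed relapse/EDSS/MRI (Gd+ or" new/enlarging T2 lesions) at any of Months 6, 12 and 18. The one exception is for participants who showed activity: "new/enlarging T2 lesions) at Month 6, 12 or 18, unless they showed disease activity". SAP 2.5.3 repeats the condition ("relapse/EDSS/MRI (Gd+ or new/enlarging T2 lesions) was missed at Month 6, 12 or 18"), and so does SAP 2.5.4. None of the three sections exempts gadolinium at Month 12, and none defines *missed*.

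**The gadolinium schedule.** SAP Table 1 gives "T1 gadolinium (Gd) @ Baseline, Month 6, 18 and T1/T2 @ every timepoint". Protocol Table 2-1 agrees: "Baseline, month 6, 18 and T1/T2 @ every timepoint". Protocol 4.5 says that the study was designed to "reduce the number of MRI scans using gadolinium". The MRI row of protocol Table 8-1 shows a Month 12 scan for ofatumumab participants without separating enhanced from unenhanced imaging. Its gadolinium footnote concerns healthy controls only: "Gadolinium will not be given to healthy controls and gadolinium enhanced T1 MRI imaging will not be conducted in healthy controls".

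**The endpoint.** In SAP 2.5.1, "MRI activity-free is defined as no Gd+ lesions on any MRI scan (scheduled or unscheduled) after Month 6", together with no new or enlarging T2 lesions relative to Month 6 on any later scan. SAP 2.5.2 analyses NEDA-3 in the mFAS with a Clopper-Pearson interval.

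**The concern.** The clause pairs Gd+ with Month 12, where the objectives tables plan no enhanced scan. It also pairs Gd+ with Month 6, where the result cannot affect NEDA-3: enhancing lesions count only on later scans, and Month 6 matters only as the T2 reference.

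This rule sets the primary denominator, and its effect runs one way. Participants with activity stay in despite gaps, so an unnecessary exclusion can remove only a responder and lower the estimate. The mFAS is also used for NEDA clinical, which has no MRI component, and for the supplementary NEDA-3 analysis whose MRI component is T2 only. A gadolinium gap could therefore exclude people from analyses that use no gadolinium data.

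**Working it through.** **Inputs.** SAP section 3.1: 100 evaluable participants, assumed NEDA-3 of 80% or 85%, 15% dropout, 118 enrolled. SAP 2.5.2: exact two-sided 95% interval. The documents give no expected mFAS size and no rate of missing readings. The splits below are illustrations with 100 completers and no other exclusions.

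**The plan's own figures.** Normal-approximation half-width: 1.96 × √(0.80 × 0.20 / 100) = 7.8 points, and 1.96 × √(0.85 × 0.15 / 100) = 7.0 points. Enrolment: 100 / 0.85 = 117.6, rounded up to 118. All three reproduce. The planned exact interval is slightly wider: 80/100 gives 70.8% to 87.3% (half-width 8.3) and 85/100 gives 76.5% to 91.4% (half-width 7.4). These are the reference values below.

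**Month 12 gadolinium under three readings of the clause.**

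1. *A gap in either Gd+ or T2 counts, planned or not.* No activity-free completer has a planned Month 12 Gd+ reading.
   - At 80%, all 80 responders leave and the 20 participants with activity stay: 0/20, upper limit 1 − 0.025^(1/20) = 16.8%.
   - At 85%: 0/15, upper limit 1 − 0.025^(1/15) = 21.8%.
   - Exception: unscheduled scans are mapped to visit windows (SAP 2.4.1.1), and the Month 12 MRI window is days 271 to 450 (SAP Table 6). If 1 to 5 responders had an enhanced scan there (assumption), NEDA-3 is 1/21 = 4.8% to 5/25 = 20.0% in the 80% case, or 1/16 = 6.3% to 5/20 = 25.0% in the 85% case.
2. *Only a planned reading can be missed.* Nobody is lost for Month 12 gadolinium. The result stays 80/100 or 85/100.
3. *MRI is missed only if neither Gd+ nor T2 is available.* Again nobody is lost. But a completer with a Gd+ reading and no T2 reading at Month 18 also stays, and could be counted as NEDA-3 with that component unread.

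**Month 6 gadolinium.** This matters under readings 1 and 2, where a gap in a planned Gd+ reading counts; under reading 1 the Month 12 loss already dominates. Suppose a fraction *m* of completers lacks Month 6 Gd+ but has a usable T2 reference, independently of outcome (assumption). Only responders are dropped, so the estimate becomes p(1 − m) / (1 − pm).

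| m (assumed) | Responders lost, of 80 | NEDA-3 | Exact 95% half-width |
|---|---|---|---|
| 0% | 0 | 80/100 = 80.0% | 8.3 points |
| 5% | 4 | 76/96 = 79.2% | 8.6 points |
| 10% | 8 | 72/92 = 78.3% | 8.9 points |

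The loss at 5% is 4 participants, not 5, because the one expected among the 20 with activity is kept. For the same reason the proportion shifts as well as the precision.

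**The case against.** The strongest reply is that *missed* ordinarily means that a planned assessment was not done, and that the words in parentheses can mean that either reading makes the MRI available. On both views Month 12 gadolinium removes nobody. The SAP adapts elsewhere to gadolinium that is withheld by design: SAP 2.6.1 uses a T2-only derivation where healthy controls are included. This makes a self-defeating Month 12 rule unlikely to be intended. A primary result near zero beside an ordinary observed-case result in the FAS (SAP 2.5.6) would also reveal a programming misreading, and the analysis is descriptive with no hypothesis test.

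Much of this stands. A reader might infer that the plan forces NEDA-3 to 0%, or that every activity-free completer is lost. The documents do not support either. That outcome needs one particular reading of an undefined word, and unscheduled enhanced scans would be exceptions even then. Nor can one say flatly that Month 12 gadolinium is never scheduled: this rests on the two objectives tables, because Table 8-1 does not distinguish enhanced scans.

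On Month 6, gadolinium is planned at that visit, and asking for a complete re-baseline scan is a defensible strictness. The documents give no sign of how often Gd+ would be missing while T2 is usable.

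The reply does not remove the mismatch. The benign readings are written nowhere, and they differ on which gaps exclude a participant. The non-response analysis does not settle it, because SAP 5.1.3.3 asks for a complete set of assessments without saying which MRI readings that includes.

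**Conclusion.** The concern holds as a conflict between the primary-denominator rule and the trial's own imaging schedule, and as an unnecessary Month 6 requirement.

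- **Month 12.** The effect ranges from none (only planned readings can be missed, or either reading suffices) to near-total loss of responders (any gap counts; 0/20 at the assumed 80%, exact interval 0% to 16.8%). The first is the more natural intention, but the text does not fix it.
- **Month 6.** Where a gadolinium gap counts, the bias is downward and small: about 0.8 points at 5% missing and 1.7 points at 10%, with the half-width up by about 0.3 and 0.6 points. This rests on 100 completers, 80% NEDA-3, missingness unrelated to outcome and assumed missing rates.

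This should be corrected before database lock. The likely numerical effect is modest, but the membership of the primary analysis set should not depend on how a programmer reads one word.

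**What to change.** In SAP 2.2, 2.5.3 and 2.5.4, replace the MRI clause with the readings the endpoint uses: an evaluable Month 6 scan as the T2 reference, new/enlarging T2 at Months 12 and 18, and Gd+ at Month 18. Add that a reading not scheduled at a visit is not counted as missed. The exception for participants who showed activity can stay as it is.

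The cost is one sentence in three SAP sections, with no change to imaging or data collection. The trade-off is slightly less strict completeness at the Month 6 re-baseline scan, where a missing Gd+ reading would no longer exclude a participant.

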### **2.2.1 Subgroup of interest**

There is no subgroup analysis planned for this study.

## **2.3 Patient disposition, demographics and other baseline characteristics**

### **2.3.1 Patient disposition**

Participant disposition will be summarized for the following disposition events using all screened participants:

- Screening period
- Open-label treatment phase
- Open-label extension period
- Study

Participants who have discontinued from the study will be listed as appropriate along with the primary reason for discontinuation.

The number and percentage of screen failures and the reason for screen failure will be presented for all screened participants.

For each protocol deviation, the number and percentage of participants for whom the deviation applies will be summarized by Cohort for the open-label treatment phase, open-label extension period and overall using the FAS or HCAS, as appropriate.

### **2.3.2 Demographics and other baseline characteristics**

The following demographic and baseline characteristic variables will be summarized descriptively by Cohort using the FAS or HCAS, as appropriate:

#### **Continuous variables**

- Age (years)
- Height (cm)
- Weight (kg)
- Body mass index (BMI) (kg/m^2) [weight (kg) / height (m^2)]

#### **Categorical variables**

- Sex (Male, Female, Unknown, Undifferentiated)
- Ethnicity (Hispanic or Latino, Not Hispanic or Latino, Not reported, Unknown)
- Race (White, Black or African American, Asian [Chinese, Indian, Japanese, Korean, Vietnamese, Other], Native Hawaiian or Other Pacific Islander, American Indian or Alaska Native, Unknown, Multiple)

- Smoking status (Former, Current, Never) by type of substance (Tobacco, Marijuana, Vape); former smoker of any type of substance; current smoker of any type of substance

### 2.3.3 MS history

The number and percentage of participants with 0, 1, 2 or  $\geq 3$  relapses in the last 12 months prior to screening will be presented using the SAF. In addition, the number and percentage of participants with at least 1 relapse will be presented.

The following variables will be summarized descriptively as continuous variables using the SAF:

- Time (days) from onset of most recent relapse to first dose of ofatumumab [(date of first dose of ofatumumab – date of onset of most recent MS relapse) + 1]
- Time (years) from RRMS diagnosis to first dose of ofatumumab [(date of first dose of ofatumumab – date of RRMS diagnosis) + 1]/365.25
- Time (years) from first MS symptoms to first dose of ofatumumab [(date of first dose of ofatumumab – date of first MS symptoms) + 1]/365.25
- Baseline EDSS score

Partial most recent relapse onset dates, RRMS diagnosis dates and first MS symptoms dates will be imputed as outlined in [Section 5.1.3.3](#).

### 2.3.4 Medical history

Medical history will be coded using the Medical Dictionary for Regulatory Activities (MedDRA) terminology. The MedDRA version used for reporting the study will be indicated in a footnote on relevant outputs.

Medical history will be summarized with frequency counts and percentages by Cohort, primary system organ class (SOC) and preferred term (PT) using the SAF or HCAS, as appropriate. Tables will show the overall number and percentage of participants with at least one reported medical history event in a particular primary SOC and at least one reported medical history event in a particular PT.

